9.4.3 ANALYSIS OF THE SECONDARY ENDPOINT(S)

We will calculate distributional characteristics and perform a two-group intent to treat analysis for continuous or ordinal endpoints using 2-sided t-tests or analysis of variance (ANOVA) with Type I error rate alpha= 0.05, and risk differences or mean differences with confidence intervals for quantification and estimation of effect.

Secondary endpoint	Dependent on primary endpoint?	Repeated measure?	Scale	Statistical procedures
Decision confidence	No	No	Continuous	2-sided t-tests
Anxiety – STAI Brief	No	Yes: Pre and Post	Continuous	2-sided t-tests
Thyroid Cancer Fear	No	Yes: Pre and Post	Continuous and Ordinal	2-sided t-tests and ANOVA
Patient Perception of Physician Empathy	No	No	Continuous	2-sided t-tests
Trust in Physician	No	No	Continuous	2-sided t-tests
Information recall	No	No	Continuous	2-sided t-tests

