1 PROTOCOL SUMMARY

1.1 SYNOPSIS

Title: The effect of surgeon emotional support on treatment choice for low-risk thyroid cancer: a randomized hypothetical choice experiment

[figure not shown]
Grant Number: K08CA230204

Study Description:	In this study, we will test the extent to which emotionally supportive communication from a surgeon is associated with patient preference for total thyroidectomy. We will conduct a hypothetical choice experiment with “analogue” patients, defined as those with a benign thyroid nodule not requiring surgery. We will collect baseline measures, then randomize participants to watch a video simulation of a patient-surgeon discussion about treatment options for low-risk thyroid cancer with or without emotionally supportive statements. We hypothesize that increased emotionally supportive communication by the surgeon will decrease the likelihood of patients choosing total thyroidectomy, reduce anxiety and thyroid cancer fear, and increase decisional confidence, perceived physician empathy, trust in physician, and information recall.
Objectives[*]:	
Primary Objective: Test the extent to which emotionally supportive communication by a surgeon is associated with patient preference for total thyroidectomy.
 
Secondary Objectives: Test the extent to which emotionally supportive communication by surgeons is associated with anxiety, thyroid cancer fear, perceived empathy, physician trust, and decisional confidence.
 
Tertiary/Exploratory Objectives: Test the extent to which emotionally supportive communication by a surgeon is associated with information recall.

Endpoints[*]:	
Primary Endpoint: Hypothetical treatment choice immediately after watching the video intervention
 
Secondary Endpoints: state anxiety, thyroid cancer fear, decisional confidence, perceived physician empathy, physician trust immediately after watching the video intervention
 
Tertiary Endpoint: information recall immediately after watching the video intervention

Study Population:	118 adults with benign thyroid nodules who were seen at a UW Health clinic for a fine needle biopsy and do not need surgery
Phase[*] or Stage:	N/A
Description of Sites/Facilities Enrolling Participants:	Single-site study at University of Wisconsin-Madison, including biopsy clinics at UW Health at the American Center, 1 South Park, and UW Hospital & Clinics

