3 OBJECTIVES AND ENDPOINTS

OBJECTIVES	ENDPOINTS	JUSTIFICATION FOR ENDPOINTS
Primary		
Test the extent to which increased emotionally supportive communication by surgeons is associated with patient preference for total thyroidectomy.	We will measure which treatment participants would choose if they were the patient with thyroid cancer in the video (total thyroidectomy or hemithyroidectomy) immediately after they finish watching the video.	Treatment choice is the primary endpoint because prior studies in different populations indicate increased emotional support can influence medical choices. Emotionally supportive communication is most likely to impact patient preference in the short-term, as the treatment decision is being made.
Secondary		
Test the extent to which increased emotionally supportive communication by surgeons is associated with anxiety, thyroid cancer fear, perceived empathy, trust, and decisional confidence.	We will measure these endpoints immediately after participants finish watching the video, using the State Trait Anxiety Inventory brief, an adapted Cancer Fear Scale an adapted Trust in Physician Scale, an adapted Jefferson Scale of Patient's Perceptions of Physician's Empathy, and decisional confidence using a single-item 10-point Likert scale.	These secondary endpoints were selected because they represent potential emotion-related outcomes in the treatment decision-making process. Prior studies indicate the increased emotionally supportive communication can influence these outcomes in other medical settings.
Tertiary/Exploratory		
Test the extent to which increased emotionally supportive communication by surgeons is associated with information recall.	We will assess information recall immediately after participants finish watching the video with 5 multiple choice questions that ask about information relayed in both intervention videos.	Published data suggest that heightened emotional states can inhibit information processing and recall. Response to this heightened state with increased emotional support may improve recall.

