9 STATISTICAL CONSIDERATIONS

9.1 STATISTICAL HYPOTHESES

Primary Endpoint: We hypothesize that emotionally supportive communication will decrease patient preference for total thyroidectomy immediately after watching the video.

Secondary Endpoints: We hypothesize that emotionally supportive communication will decrease anxiety and thyroid cancer fear and increase trust, perceived empathy, and decisional confidence immediately after watching the video.

Tertiary/exploratory: We hypothesize that emotionally supportive communication will increase information recall immediately after watching the video.

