9.2 SAMPLE SIZE DETERMINATION

We assume based on existing data that the proportion of participants choosing total thyroidectomy will be 0.89 and estimate the sample size needed for 90% power to detect a proportion lower than 89%. With a sample of n=59 in each group, we will be able to detect risk differences of -25% and medium effect sizes of -0.60 with 90% power using a 2-sided test (chi square for binary outcome) with Type I error rate alpha= 0.05. The UW Thyroid Nodule Biopsy clinic performs over 500 biopsies annually, of which approximately 70% are benign. The UW Radiology clinic performs 400 biopsies per year on patients with benign thyroid nodules.

We anticipate missing data will be very low as the study is expected to be completed in one sitting.

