9.4 STATISTICAL ANALYSES

9.4.1 GENERAL APPROACH

For descriptive statistics, categorical and continuous data will be presented as percentages, means with standard deviations, median, and range. For inferential tests, we will use 2-sided tests with Type I error rate alpha=0.05 for statistical significance. Covariates are specified below. Checks for assumptions of normality will be performed. If data are not normal, nonparametric tests will be used.

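### Anxiety and thyroid cancer fear have a pre-randomisation score that the comparison in 9.4.3 does not use; baseline-adjusted ANCOVA would be more precise unless the pre-post correlation is near zero

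*Combined protocol and SAP*

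**What the plan says.** Sections 4.1 and 8.1 place the STAI-6 and the adapted thyroid cancer fear scale in the survey completed before randomisation and again among the post-video measures. The STAI-6 total runs from 6 to 24 and the fear total from 8 to 40.

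For the secondary endpoints, section 9.4.3 will "perform a two-group intent to treat analysis for continuous or ordinal endpoints using 2-sided t-tests or analysis of variance (ANOVA", with mean differences and confidence intervals. In its table, anxiety and fear are the only rows marked "Yes: Pre and Post" as repeated measures. The procedures listed are t-tests for anxiety, and t-tests plus ANOVA for fear, which is labelled both continuous and ordinal. No baseline covariate, change score or repeated-measures model is named.

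Section 9.4.1 announces "Covariates are specified below". The one adjustment that follows is for sex, in the primary analysis (9.4.2). Section 9.4.1 also says "If data are not normal, nonparametric tests will be used", without saying what becomes of the baseline score. In section 9 the baseline anxiety and fear scores are otherwise used only to describe the sample (9.4.5).

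The endpoints are worded as post-video values: "physician trust immediately after watching the video intervention" closes the list in the synopsis, section 3 has "We will measure these endpoints immediately after participants finish watching the video", and section 9.1 has "emotionally supportive communication will decrease anxiety and thyroid cancer fear and increase trust, perceived empathy, and decisional confidence immediately after watching the video".

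**The concern.** A score on the same scale, taken minutes before randomisation, is usually the best available predictor of the post-video score. Using it as a covariate removes the part of the between-person variation that it explains. The plan collects it and then leaves it out of the comparison. Anxiety and fear are the route by which support is supposed to change treatment choice (sections 2.1 and 2.2), so the width of these two confidence intervals matters to the interpretation of the trial.

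The text also leaves the analysis open. The repeated-measure flag is compatible with a t-test on the post-video score or on the change, and these can differ considerably in power. The same gap exists in the non-normality fallback, which could well be triggered because both scales are bounded sums. A choice left open can be made after the data are seen.

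**Working it through.** **Inputs from the documents.** 59 per arm, two-sided alpha 0.05, standardised effect 0.60, 90% power (9.2, 9.4.1); 1:1 allocation within sex (6.3).

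**Assumed.** Pre-post correlation r of 0.3, 0.5, 0.7 or 0.8, equal SDs and a common slope in the two arms. The documents give neither r nor the SDs.

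**The plan's own figure.** Section 9.2 claims "medium effect sizes of -0.60 with 90% power". For a two-sample t-test with 59 per arm, the noncentrality is 0.60 / √(2/59) = 0.60 / 0.184 = 3.26 on 116 df. Power is 89.8%, and 90.3% by the normal approximation. The figure reproduces and corresponds to an unadjusted comparison. The effect detectable with exactly 90% power is 0.602 SD. The 95% CI half-width is 1.981 × 0.184 = 0.365 SD.

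**Formulas.** Variance of the treatment contrast relative to the post-video t-test:

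- ANCOVA: 1 − r²
- Change score: 1 + 1/k² − 2r/k, where k is the post/pre SD ratio; this is 2(1 − r) when k = 1

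The ANCOVA has arm, baseline and sex in the model (114 df). No precision is credited to sex.

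| | Post-video t-test | ANCOVA r=0.3 | r=0.5 | r=0.7 | r=0.8 |
|---|---|---|---|---|---|
| Relative variance | 100% | 91% | 75% | 51% | 36% |
| 95% CI half-width (SD) | 0.365 | 0.348 | 0.316 | 0.260 | 0.219 |
| Detectable at 90% power (SD) | 0.602 | 0.574 | 0.521 | 0.430 | 0.361 |
| Power at 0.60 SD | 89.8% | 92.3% | 96.2% | 99.5% | >99.9% |
| Power at 0.40 SD (illustrative) | 57.7% | 61.7% | 70.1% | 85.5% | 94.8% |

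**Lower limit.** Chance baseline imbalance inflates the ANCOVA variance by a factor of about 1 + 1/113, or 0.9%. At r = 0 the detectable effect is then 0.605 SD against 0.602 SD. Break-even is at r of about 0.09. At r = 0.3 the allowance lowers power at 0.60 SD from 92.3% to 92.1%.

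**Simulation on normal data.** With 20,000 trials per r and baseline and sex in the model, power at 0.60 SD was 92.4%, 96.1%, 99.4% and 100%, in line with the formulas. Type I error was 4.6% to 5.0%.

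**If the change score is meant.** At equal SDs:

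| | r=0.3 | r=0.5 | r=0.7 | r=0.8 |
|---|---|---|---|---|
| Change-score relative variance | 140% | 100% | 60% | 40% |
| Change-score power at 0.60 SD | 78% | 90% | 98.7% | 99.9% |
| Change-score power at 0.40 SD | 44% | 58% | 79% | 93% |

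ANCOVA is better in every column, but only slightly at high r. With unequal SDs the two can nearly tie: at r = 0.7 and k = 1.3 the change-score variance is 1 + 1/1.69 − 1.4/1.3 = 51.5%, against 51.0% for ANCOVA.

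**Fallback.** The test case is a right-skewed integer score clipped to 6–24, with a latent effect of 0.60 SD and 20,000 trials per r. A Mann-Whitney-type test on post-video scores had 87% to 88% power. Rank-based ANCOVA had 90%, 94%, 99% and 100%, with type I error of 4.8% to 5.0%. The distribution is invented for illustration; it shows only that the gain survives skewness and bounds.

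**The case against.** The strongest objection is to the comparator. Section 9.4.3 never says that the t-test uses the post-video score. A column that singles out these two scales as pre-and-post has little purpose if the pre score goes unused. Section 4.1 justifies the STAI-6 by its ability to register change in experiments of this type, and the ANOVA for fear could mean a group-by-time analysis. If change scores are intended, the gain at high correlation is small: 98.7% against 99.5% power at r = 0.7 and 0.60 SD. This stands as a limit on the size of the gain. It does not remove the point, because ANCOVA is then still clearly better at r of 0.5 or below, and the doubt over which score is meant is itself a defect.

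The gain also rests on an unknown r. The baseline is taken after a benign result and the post score after a cancer scenario, so the correlation could be low. At r = 0.3 the gain at the plan's own effect is only 2 points, and the 0.40 SD scenario is not in the plan. That is fair. Against it, the same scale is repeated in one sitting, which makes a value below 0.09 unlikely, and the worst-case cost is about 1% of variance.

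The covariate sentence in 9.4.1 is arguably met by the adjustment for sex in 9.4.2. It shows that no covariate reaches these two scales, not that the plan contradicts itself. Finally, rank-based ANCOVA does not yield the mean difference that 9.4.3 promises. A fallback using bootstrap or robust standard errors does.

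**Conclusion.** The concern holds. Section 9.4.3 names no baseline term for two endpoints that have a baseline score, and ANCOVA would estimate the same mean difference more precisely than the post-video t-test unless r is below about 0.09. For r between 0.3 and 0.8, the CI half-width shrinks from 0.365 SD to between 0.348 and 0.219 SD. Power at 0.60 SD rises by 2 to 10 points. Against a change-score t-test the gain ranges from substantial at low r to nearly nil at high r or some SD ratios.

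These sizes depend on assumed correlations, equal SDs in the main table and a common slope. The planned t-test is valid, so this is lost precision and an open choice of analysis, not bias. It concerns two secondary endpoints only. The change should be made because it costs nothing, but the trial does not depend on it.

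**What to change.** In section 9.4.3, for the STAI Brief and Thyroid Cancer Fear total scores:

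1. Make the main analysis an ANCOVA of the post-video score on arm, baseline score of the same scale, and sex. Sex is included because it is the stratification factor and is already accounted for in the primary analysis, not for added precision.
2. Report the adjusted mean difference with its 95% CI.
3. State that for these two scales the non-normality fallback in 9.4.1 keeps the baseline adjustment. ANCOVA with bootstrap or robust standard errors retains the mean difference; rank-based ANCOVA is an alternative if only a test is needed.
4. Keep the planned analysis of ordinal fear categories as supporting.

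The cost is SAP wording. Baseline scores and sex are already collected before randomisation, so no data, participants or procedures are added, and the sample size stays at 118.

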Potentially eligible patients will arrive to clinic, undergo needle biopsy of their thyroid nodule, and receive a study brochure. Cytology results are automatically released to patients via MyChart and the ordering physician calls the patient within 24-48 hours with their results. Once a benign diagnosis and eligibility is confirmed via chart review, we will approach patients and enroll interested participants within 30 days of their diagnosis. Patients will complete the study in one sitting on a computer or tablet in their own home by accessing a Qualtrics link at a time that is convenient for them. They will confirm their eligibility through screening questions and then proceed to the information page with consent language. If they have questions about the information page, they are directed to contact the study team before indicating consent. Once they indicate consent they will proceed to the pre-intervention survey (administered prior to randomization) which will include demographics (sex assigned at birth, age, race, ethnicity, education, personal cancer history, clinical history regarding their recent biopsy, and baseline measures including the STAI-6 and thyroid cancer fear scale.^{47,48} Participants will then get randomized by Qualtrics to a study arm. After viewing the video, they will complete measures including the STAI-6, an adapted cancer fear scale, manipulation check, physician empathy scale, trust in physician scale, a 5-question information recall questionnaire about the treatment options discussed in the video, and the following questions: (1) “If you were the patient in the video, which treatment option would you choose for yourself?” and (2) “How confident do you feel that you would be choosing the best treatment option for you?” on a 10-point scale [not at all confident to completely confident].⁴⁷⁻⁵⁰ Our primary outcome is treatment choice: total or hemi-thyroidectomy. We chose the STAI-6 because of its predictive validity in assessing changes induced by hypothetical choice experiments in patients with cancer.^{41,45} Our post-intervention measures are further described in **Section 8.1**. Participation is expected to take less than 30 minutes to complete.

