N/A	Manipulation check	Post-intervention	We will assess patients' engagement with the video with 5 items. Questions will ask about concentration and the extent to which the patient could identify with various aspects of the video. Response options are on a 7-point Likert scale ranging from 'completely disagree' [1] to 'completely agree' [7].
Secondary	Anxiety – STAI Brief	Baseline and Post-intervention	This 6-question, quantitative instrument was designed to assess state anxiety. ⁴⁷ Response options are on a 4-point Likert scale ranging from 'not at all' [1] to 'very much' [4]. Scores are totaled with a potential range of 6 to 24. We chose the STAI-6 because of its predictive validity in assessing changes induced by hypothetical choice experiments in patients with cancer. ^{41,45}
Secondary	Thyroid Cancer Fear (adapted)	Baseline and Post-intervention	This 8-question quantitative instrument was originally designed to assess fear of breast cancer in patients undergoing cancer screening. ⁴⁸ Items are rated on a 5-point scale from strongly disagree [1] to strongly agree [5]. We will adapt the measure to assess participants' fear of thyroid cancer. The score ranges from 8 to 40. For the original scale, low fear was defined as a total score of 8 to 15, moderate fear as a score of 16 to 23, and high fear as a score of 24 to 40.
Secondary	Jefferson Scale of Patient's Perceptions of Physician	Post-intervention	This 5-question quantitative instrument assesses patient perceptions of physician empathy. ⁵² Minor adaptations in wording were made to fit the video scenario. Response options are on a 7-point Likert scale ranging from

	Empathy (adapted)		'strongly disagree' [1] to 'strongly agree' [7]. Items are summed, with a max score of 35, and higher values indicating a perception of more empathy.
Secondary	Trust in Physician Scale (adapted)	Post-intervention	This 5-question quantitative instrument assesses patient trust in a physician. ⁴⁹ Response options are on a 5-point Likert scale ranging from 'strongly disagree' [1] to 'strongly agree' [5]. Responses are summed and scores are on a scale of 5 to 25, with higher values indicating more trust.

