9.4.2 ANALYSIS OF THE PRIMARY ENDPOINT(S)

The primary endpoint, treatment choice, is a binary scale. It will be measured once immediately after the intervention.

We will calculate distributional characteristics and perform a two-group intent to treat analysis for this binary endpoint using conditional logistic regression to account for stratification by sex. The Type I error rate alpha= 0.05.

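### Thyroid cancer fear has one hypothesis but two listed scales and two listed tests, with no rule for which decides; one baseline- and sex-adjusted comparison of the total score should replace them, and the same model suits STAI

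*Combined protocol and SAP*

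**What the plan says.** All references are to the combined protocol and SAP.

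- **Hypothesis (9.1).** One directional statement covers fear: "emotionally supportive communication will decrease anxiety and thyroid cancer fear".
- **Analysis (9.4.3).** The table has six rows. Five list one scale and t-tests only. The fear row lists the scale as "Continuous and Ordinal" and the procedures as "2-sided t-tests and ANOVA". The sentence above the table joins t-tests and ANOVA with *or*, at alpha 0.05. Fear and STAI are both marked as measured before and after the video.
- **Scale (8.1).** The fear total runs from 8 to 40. Bands are described, but only for the source instrument: "For the original scale, low fear was defined as a total score of 8 to 15", with moderate at 16-23 and high at 24-40. The trial uses an adapted version.
- **Covariates (9.4.1, 9.4.2).** The general approach says "Covariates are specified below". What follows is the primary analysis, which uses "conditional logistic regression to account for stratification by sex". No covariate is named for any secondary endpoint.
- **Data available (4.1).** The survey completed before randomization includes "baseline measures including the STAI-6 and thyroid cancer fear scale". Sex is also recorded there and is the stratification factor.

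**The concern.** A single hypothesis should have a single deciding result. Here the plan does not say what the ANOVA is applied to, whether the t-test uses the post-video score or the change, or which of the two settles the question. If the tests use different forms of fear and disagree, either could be reported as the finding, and the error rate for this endpoint is no longer the stated 5%.

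A second, separate matter is precision. Fear and STAI each have a baseline score taken shortly before the video, and randomization is stratified by sex. The listed procedures use neither as a covariate. A change-score test would bring the baseline in, but by plain subtraction, which is less efficient than regression on it.

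**Working it through.** **Inputs from the documents.** 59 per arm, two-sided alpha 0.05, effect size 0.60 (section 9.2); score range 8-40 and band limits (8.1).

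**Assumptions, not in the documents.** All 59 per arm analysed; SD 6-8; mean fear 16-28 for error rates and 20 or 24 for power; pre-post correlation r of 0.4-0.8; normal scores rounded and limited to 8-40; for the adjusted model, 46 of 59 per arm female and a sex effect of 0 or 0.3 SD.

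**Step 1. Reproduce the plan's figure.** Section 9.2 claims "medium effect sizes of -0.60 with 90% power". The normal formula gives n = 2(1.960 + 1.282)² / 0.60² = 58.4, so 59 per arm. Power at 59 is 0.903 (normal) or 0.898 (noncentral t). The figure holds for an unadjusted t-test.

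**Step 2. Error rate by reading.** Chance of at least one p<0.05 in either direction when there is no effect, 59 per arm, 20,000 simulated trials per scenario:

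| Reading | Either test significant |
|---|---|
| t-test and one-way ANOVA on the same total | 5% (F = t² with two arms; p-values differed by at most 2e-15) |
| t-test on total plus ANOVA on bands | 6.6-8.4% (each test alone 4.6-5.3%) |
| Both on change (group-by-time ANOVA equals the change t-test) | 5% |
| Post-score t-test plus group-by-time ANOVA | 8.4-10.1% |

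A separate rerun of the bands reading under the same assumptions gave 6.4-8.1%, which agrees within simulation error.

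**Step 3. Which reading is natural.** Section 9.4.3 speaks of continuous or ordinal endpoints and of t-tests or ANOVA. The only row marked ordinal is the only row with ANOVA, and section 8.1 describes only one ordinal form of the fear score, the bands. STAI is also pre/post but lists t-tests only, so ANOVA does not appear to stand for repeated measures. That points to the second row of the table. It remains an inference.

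**Step 4. Direction.** The rates in step 2 count both directions. Halving gives 6.6/2 = 3.3% to 8.4/2 = 4.2% for a false finding of reduced fear, against a nominal 2.5%. Counted directly in the rerun, it was 3.2-4.1%.

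**Step 5. Power.** Power is about Φ(d√(n/2)/s − 1.960), where s is the SD of the analysed quantity relative to the score SD: 1 for the post score, √(2(1−r)) for change, √(1−r²) with baseline as a covariate. With d = 0.5 and n = 59, d√(n/2) = 0.5 × 5.431 = 2.716. At r = 0.5:

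- post score: s = 1, Φ(0.756) = 0.775;
- change: s = 1, Φ(0.756) = 0.775;
- adjusted: s = 0.866, Φ(1.176) = 0.880.

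Simulation with rounding and the 8-40 limits (10,000 trials per scenario) gives slightly lower values:

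| Effect, r | Baseline and sex adjusted | Post-score t-test | Change t-test |
|---|---|---|---|
| 0.5 SD, 0.4 | 0.81-0.83 | 0.74-0.77 | 0.66-0.69 |
| 0.5 SD, 0.5 | 0.86-0.87 | 0.75-0.77 | 0.73-0.77 |
| 0.5 SD, 0.8 | 0.991-0.995 | 0.75-0.77 | 0.979-0.989 |
| 0.60 SD, 0.5 | 0.95-0.96 | 0.88-0.90 | 0.86-0.90 |

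Type I error of the adjusted model was 0.044-0.054. Sex adds less than 0.002 to power; nearly all the gain comes from the baseline score.

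**The case against.** **The double listing may be harmless.** On two of the four readings the tests coincide and the error rate stays at 5%. This stands. The plan does not commit to those readings, however, and where they apply the second entry is redundant, so removing it loses nothing.

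**A reader might infer that the error rate is about 10%.** That needs a post-score test and a change test to be used together. The documents do not say so, and the ambiguity between post score and change exists equally in the STAI row. It should not be the headline.

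**A reader might infer that the listed tests necessarily discard the baseline score.** They do not if the test is on change or is a group-by-time ANOVA, and the pre/post marking keeps that possible. What holds is that baseline is not a covariate. Against a change test, the gain from adjustment shrinks to about 1-2 points at correlation 0.8. With both measures taken in one short sitting, a high correlation cannot be ruled out.

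**A reader might infer that unadjusted tests are invalid here, or that fear alone lacks adjustment.** Neither is so. In the simulations the unadjusted tests held their size (0.046-0.054), so adjustment is a matter of efficiency. Baseline adjustment is equally absent for STAI, and sex adjustment for every secondary endpoint. Only the double listing is peculiar to fear.

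**Nonparametric fallback.** Section 9.4.1 sends non-normal data to nonparametric tests, and three bands cannot be normal. A rank test on the bands gave a similar rate for either test significant (6.9-8.4%), so the conclusion does not turn on this.

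**Adjustment has a cost.** Section 2.3.3 lets participants skip questions. A skipped baseline item would drop a person from the model unless a rule is set. This stands, and the fix includes a rule.

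**Conclusion.** The point holds as a minor one about secondary endpoints. The fear row gives one hypothesis two scales and two tests without saying which decides. On the most natural reading, the two-sided chance of a false positive for this endpoint is about 6.6-8.4% rather than 5%, or about 3.3-4.2% rather than 2.5% for a false finding of reduced fear. On the readings where the tests coincide there is no inflation.

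Separately, for fear and STAI the plan forgoes covariate adjustment that would raise power by roughly 10 points over either simple test at a 0.5 SD effect and correlation 0.5. At correlation 0.4 the gain over a post-score test is smaller, about 6 to 7 points. At 0.8 it is large over a post-score test and slight over a change test.

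The means, SDs and correlations are assumed, so the sizes are illustrative; the ambiguity in the table does not depend on them. The primary endpoint and the 59 per arm are unaffected.

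**What to change.** Before outcome data are examined:

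1. Make the post-video fear total (8-40) the single tested fear outcome. Report one between-arm mean difference with a 95% CI from a linear model with arm, baseline fear and sex.
2. In the fear row of 9.4.3, delete the ordinal scale and the ANOVA, and name this model in place of the t-tests.
3. Report low, moderate and high fear by arm descriptively, noting that the cut-points come from the original scale.
4. Use the same model for STAI, with its own baseline score and sex.
5. Bring the sentence above the 9.4.3 table and the covariate statement in 9.4.1 into line.
6. State a rule for a skipped baseline item, for example imputing the overall mean of the baseline covariate, so that no randomized participant with a post-video score is dropped.

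The cost is minor wording and a little analysis work. No new data and no additional participants are needed, because baseline fear, baseline STAI and sex are already collected before randomization.
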